### **HIPAA Release Form**

HIPAA release document will be part of the informed consent document.

## **5.4 Inclusion/Exclusion Criteria**

### **Inclusion Criteria:**

- Subject must be 18 years old or older
- NYHA (New York Heart Association Functional Classification) Class II-IV, documented in site's medical record system.
- Subject able and willing to sign Informed Consent Document.
- Subject willing and able to perform all study related procedures.

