## Abstract

The study comprises of 1) the **main experimental procedures** to assess efficacy of early intervention based on alarms generated from data collected by the continuous wearable monitoring system on prevention of hospitalization due to heart failure exacerbation, with 240 participants and 2) the **non-experimental procedures for implementation research and qualitative research** based on **interviews and focus groups** consisting of 20 patients total and 10 clinicians/site.

For **experimental procedures**, we plan to recruit adult subjects with history of HF with reduced or preserved ejection fraction, New York Heart Association (NYHA) functional class II-IV hospitalized for HF will be eligible for study participation. Exclusion criteria include expected heart transplant or ventricular assist device implant within 90 days of enrolment, skin damage preventing use of study device, and visual or cognitive impairment that precludes ability to comply with study procedures. The study coordinators will screen prospective study subjects. The study will be discussed in detail with patients interested in participation, informed consent obtained, and subjects enrolled at hospital discharge.

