Aim 1b. Evaluate implementation outcomes, including clinician and patient perceptions and adoption of the use of ambulatory remote monitoring data. We will use both quantitative and qualitative research methods to examine the eight core dimensions of implementation outcomes. Focus groups and semi-structured interviews will be done to assess clinician and patient perceptions of acceptability and feasibility. We plan to enroll up to 10 clinicians per site and 20 patients for this qualitative part of the study. Adoption behaviors will be tracked including alert response rates and appropriateness of decisions. Fidelity of implementation will be monitored by assessing compliance with all aspects of the study protocol. Penetration and sustainability will be evaluated by assessing variation in implementation outcomes across the five study sites as well as participant perceptions from the qualitative work at the end of the study.

Aim 2. Conduct a feasibility study of non-invasive remote monitoring in chronic HF.

Aim 2a. Define key characteristics that will inform design of a pivotal trial of non-invasive remote monitoring aimed at reducing rehospitalization and improving quality of life in HF. We will enroll a total of 240 patients between five VA centers hospitalized for HF exacerbation. At enrollment, subjects will undergo 1:1 randomization to intervention or control arm. While all study subjects will use the monitoring device for 90 days after discharge, in the intervention arm, clinicians will be notified of clinical alerts and will follow the response algorithm to modify HF treatment and/or recommend urgent clinic visit/emergency room visit. In the control arm, information from the sensor will be collected, but clinical alerts will not be generated or communicated to providers. The main study outcomes will include the proportion of randomized patients who meet the algorithm's criteria for at least one alert, the proportion of time the remote monitor is in use and functioning properly, HF hospitalization rate, length of hospital stay, and health-related quality of life. Implementation factors identified in Aim 1 will help clarify the results of this aim.

Aim 2b. Identify costs associated with implementation and clinical use of non-invasive remote monitoring in HF. Correct classification of costs associated with implementation of non-invasive remote monitoring will set the stage for cost-effectiveness analyses in a future pivotal trial.

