Recent advances in technology and in machine learning provide an opportunity for processing of new sources of real-time patient-level data to generate clinically actionable information. An important knowledge gap is how to best implement this technology-based approach into clinical practice. Our study addresses this critical question of clinical implementation and will generate feasibility data for a design of a pivotal clinical trial of non-invasive remote monitoring with predictive analytics during the high-risk period after hospital discharge. This work has potential to result in changes to care of Veterans with HF and other chronic health conditions.

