## 5.0 Study Procedures

### 1). Experimental Procedures

**Participant Identification:** We will identify patients for inclusion in the study during hospitalization at the VA hospital prior to discharge or during routine clinic visits at the Heart Failure/Cardiology Clinic. The principal investigator ([name]) or the research coordinator ([name]) or the co-investigator will approach the patients in the hospital during their

stay or at the Heart Failure/Cardiology Clinic to discuss participation in this study. Charts will be screened at study locations for diagnosis of heart failure. Patients with such diagnosis will be approached in person by the aforementioned study team members and told about the study. If the patient is interested, further review will be completed with them all in a confidential manner.

**Participant Recruitment and Training:** All patients admitted to VA Medical Center in Salt Lake City with heart failure or seen in the Heart Failure Clinic or General Cardiology Clinic, who meet eligibility criteria, will be screened by a research coordinator, PI and Co-investigators. Patients meeting eligibility criteria will be approached regarding participation in this study. The PI and the other sub-investigators will be responsible for the care of these patients when they get admitted to the hospital or seen in the clinic. The PI, the Co-investigators and study coordinators will invite the potential participants into the study (if they meet inclusion/exclusion criteria) and explain to them the procedure in detail. If the patients agree to participate in the study, they will be asked to sign the consent form. We are not planning to post flyers or send recruitment letters. Follow-up phone calls will be made within one week to one month after enrollment.

After consenting, all subjects will be trained on placement of the device on the skin with supervision, guidance, and directions from the study team. The subject will have ample time to try the device themselves as the site will have extra adhesives and inactive devices for the purposes of demonstration. Subjects may be trained and fitted as hospital in-patients and re-trained in clinic when necessary. Written take-home instructions will also be provided.

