## 5.3 Informed Consent Procedures

### CONSENT PROCESS

The potential participants who meet inclusion/exclusion criteria will be approached a few days before discharge from the hospital or at the time of their routine follow-up clinic visit at the Heart Failure Clinic. After the participants consent to join the study, the non-invasive monitoring device will be fitted to the patients. Once the patients give their verbal consent, we will obtain their written consent immediately afterwards as well. Therefore, there will be no waiting period between the consent process and the procurement of written consent. The patients will be free to ask about any details pertinent to the study. They will also be allowed several hours, if needed, to discuss with family and significant others before making the decision to participate.

We will explain to the patients that they are not obligated to participate in the study. Additionally, we will explain to them that should they choose to become a study participant, they can withdraw any time after enrollment. Furthermore, we will explain to the patients that if they refuse to participate in the study, their medical care will not be impacted, and they will receive the same medical care as planned before.

We will ensure that the patients clearly understand the study procedure. We will spend adequate time with the participants, to address all questions and concerns the patients may have. Subjects are scheduled at mutually convenient time and enrolled. Their time is not a limitation. In the event we are

unable to continue using a hospital room for research purposes we will take the individual(s) over to the outpatient area prior to leaving the facility.

For the subset of enrolled patients and for clinicians participating in semi-structured interviews as part of implementation and qualitative research, authorization documents/cover letters will be read before the interviews to confirm their willingness to participate in the interviews.

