### **Exclusion Criteria:**

- Expected LVAD (Left Ventricular Assist Device) implantation or heart transplantation in the next 30 days.
- Skin damage or significant arthritis, preventing wearing of device.
- Uncontrolled seizures or other neurological disorders leading to excessive abnormal movements or tremors in the upper body.
- Pregnant women or those who are currently nursing.
- Visual/cognitive impairment that as judged by the investigator does not allow the subject to independently follow rules and procedures of the protocol.

Subjects must meet all inclusion/exclusion criteria of the protocol; each study site will complete the eCRF in the electronic case report system within 72 hours of enrollment. Any deviation must be reported to the CIRB as per guidelines.

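### The Section 5.4 inclusion list omits the index HF hospitalization and three sections allow clinic recruitment, so the alert proportion and HF hospitalization rate may not describe the post-discharge population

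*Combined protocol and SAP*

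**What the plan says.** **Intended population.** The Abstract says that patients with a history of HF and "New York Heart Association (NYHA) functional class II-IV hospitalized for HF will be eligible for study participation", with enrollment and the start of monitoring at discharge. Aim 1a likewise invites patients when they leave hospital after an HF exacerbation. Aim 2a says: "We will enroll a total of 240 patients between five VA centers hospitalized for HF exacerbation". The closing paragraph of Section 3.0 says that the feasibility data are for a pivotal trial of monitoring "during the high-risk period after hospital discharge".

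**Eligibility list.** Section 5.4 has four inclusion items: age 18 or over; "NYHA (New York Heart Association Functional Classification) Class II-IV", as recorded at the site; consent; and willingness and ability to do the study procedures. Neither an HF diagnosis nor an HF admission is listed. The section closes with "Subjects must meet all inclusion/exclusion criteria of the protocol" and makes deviations reportable to the central IRB.

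**Recruitment route.** Section 5.0 identifies patients "during hospitalization at the VA hospital prior to discharge or during routine clinic visits at the Heart Failure/Cardiology Clinic". Section 5.2 screens Salt Lake City patients who are either admitted with HF or attending the HF or general cardiology clinic. Section 5.3 approaches patients shortly before discharge "or at the time of their routine follow-up clinic visit at the Heart Failure Clinic". Section 5.2 also explains the absence of flyers by saying that every eligible patient will be a hospital patient, which contradicts its own clinic route.

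**Analysis.** Section 5.6 calls the proportion of patients meeting the alert criteria a key parameter for the power of the pivotal trial, and names HF hospitalization as that trial's primary outcome. The alert proportion (item 1) is computed in the full randomized cohort. The proportion with an HF hospitalization is reported by arm, counted from enrollment. Nothing is reported by recruitment setting or by time since discharge.

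**The concern.** Items 1 and 3 of Section 5.6 are planning values for a trial in recently discharged patients. If sites follow Section 5.4 and the recruitment text as written, some of the 240 may be clinic patients whose last HF admission was long ago or who never had one. For them the 90-day window does not start at discharge and may miss the high-risk period altogether. A pooled estimate then averages two populations, and the plan has no step that would show this or undo it.

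There is also an operational problem. A site cannot tell from the protocol whether enrolling a clinic patient without an HF admission is permitted or is a reportable deviation.

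**Working it through.** **1. The plan's own precision figure.** Section 5.6 gives a margin of no more than ±0.063 for the alert proportion with 240 subjects, and ±0.073 with 180. The Wald half-width at p = 0.5 is 1.96 × √(0.25/n):

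- n = 240: 0.0633
- n = 180: 0.0730

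Both reproduce. (The exact binomial intervals that Section 5.6 specifies are slightly wider at p = 0.5: 0.065 and 0.075.) These margins measure sampling error only. They say nothing about a shift caused by enrolling a different population.

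**2. Shift in the alert proportion.** Let f be the clinic share and d the difference in alert proportion between post-discharge and clinic patients. The pooled estimate is low by f × d. Neither f nor d is in the documents. The shift reaches 0.063 when f = 0.063/d:

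| Assumed d | Clinic share at which the shift equals 0.063 |
|---|---|
| 0.10 | 63% |
| 0.20 | 32% |
| 0.30 | 21% |

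The shift can therefore be smaller or larger than the stated margin.

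**3. Shift in the 90-day HF hospitalization risk.** Assumptions, none from the documents: 25% after discharge; 6% or 15% in clinic recruits; clinic share 20% or 50%. Pooled risk = (1 − f) × 0.25 + f × clinic risk.

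| Clinic share | Clinic risk 15% | Clinic risk 6% |
|---|---|---|
| 20% | 0.8 × 0.25 + 0.2 × 0.15 = 23.0% | 0.8 × 0.25 + 0.2 × 0.06 = 21.2% |
| 50% | 0.5 × 0.25 + 0.5 × 0.15 = 20.0% | 0.5 × 0.25 + 0.5 × 0.06 = 15.5% |

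**4. What that would do to a pivotal trial.** Further assumptions: risk ratio 0.75, 80% power, two-sided 5%. Per arm, n = (1.96 + 0.8416)² × [p1(1 − p1) + p2(1 − p2)] / (p1 − p2)², with p2 = 0.75 × p1, rounded up.

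| Control risk used | Total N | Against 25% |
|---|---|---|
| 25% | 1,366 | – |
| 23% | 1,520 | +11% |
| 21.2% | 1,682 | +23% |
| 20% | 1,806 | +32% |
| 15.5% | 2,444 | +79% |

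Under these assumptions the pivotal trial would be oversized, not underpowered.

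**5. Precision if only the post-discharge group is used.** With a clinic share of 20%, n = 192 and the Wald half-width at p = 0.5 is 1.96 × √(0.25/192) = 0.071. With 50%, n = 120 and it is 0.089.

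**The case against.** The strongest reply is that this is a drafting inconsistency and that the trial is in practice a post-discharge trial. Much of the text supports this. The Abstract contains eligibility wording, Section 5.0 has the first device placed at an in-hospital training session and follow-up visits counted from discharge, and Section 5.2 says that all eligible patients are in hospital. The first clinic visit is due within two weeks of discharge, so some patients approached in clinic may have left hospital only recently. This stands as a reason not to read the plan as a deliberate choice to enroll stable outpatients. It does not remove the contradiction: the clinic wording in Section 5.0 sets no limit on time since discharge, and Section 5.4 is the list that subjects must meet. Nor can the Abstract be assumed to fill gaps in Section 5.4, because the two already differ on another criterion: the window for an expected assist device or transplant is 90 days in one and 30 in the other.

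A reader might infer from Section 5.4 that patients without HF could be enrolled. That goes too far. Section 5.0 screens charts for an HF diagnosis and approaches patients who have one, which largely covers the omission.

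A reader might also infer that a different clinic share in each arm would distort the risk ratio. The documents do not support this. They state 1:1 allocation and do not describe the method further, and a chance difference in mix is random error that the confidence interval already reflects.

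Finally, the illustrated risks are assumed, and at small clinic shares the shift is modest. At 20% and a 6% clinic risk it is 3.8 points, against a sampling margin of about 7.7 points in one arm (25%, n = 120). That is fair. But sampling error is reported with the estimate, and this shift would not be.

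**Conclusion.** The concern holds in a conditional form. The eligibility list, the recruitment sections and the stated aims contradict each other on whether an index HF hospitalization is required, and Section 5.6 has no analysis that would separate post-discharge from clinic recruits. The alert proportion and HF hospitalization rate may therefore not describe the population that the pivotal trial targets.

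It would be too strong to say that they will not describe it. That depends on how many clinic patients without a recent HF admission are enrolled and on how their rates differ, and the documents give neither. With an assumed post-discharge risk of 25%, clinic risk of 6% to 15% and clinic share of 20% to 50%, the pooled risk is 15.5% to 23%. If no such patients are enrolled, there is no shift. The missing index admission is the gap that matters; the missing HF diagnosis is minor.

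**What to change.** State in Section 5.4 both an HF diagnosis and an index HF hospitalization with enrollment at discharge, and bring Sections 5.0, 5.2 and 5.3 into line with the Abstract and aims. Resolve the conflict within Section 5.2 at the same time.

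If clinic recruitment is to be kept, say so in Section 5.4 and in the aims. Record recruitment setting and days since HF discharge for every subject at enrollment. Add to Section 5.6 that items 1 to 3 are reported by setting, and that the post-discharge group supplies the planning estimate for the pivotal trial.

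Cost: a protocol amendment in either case. Closing the clinic route may slow accrual, and Section 5.2 shows that a site was already added to help enrollment. Keeping it and reporting by setting needs no extra patients, but the post-discharge estimate will be less precise than the stated ±0.063: about ±0.071 with a 20% clinic share and ±0.089 with 50%. Section 5.6 should state that precision.

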### **Exclusion Criteria:**

- Expected LVAD (Left Ventricular Assist Device) implantation or heart transplantation in the next 30 days.
- Skin damage or significant arthritis, preventing wearing of device.
- Uncontrolled seizures or other neurological disorders leading to excessive abnormal movements or tremors in the upper body.
- Pregnant women or those who are currently nursing.
- Visual/cognitive impairment that as judged by the investigator does not allow the subject to independently follow rules and procedures of the protocol.

Subjects must meet all inclusion/exclusion criteria of the protocol; each study site will complete the eCRF in the electronic case report system within 72 hours of enrollment. Any deviation must be reported to the CIRB as per guidelines.

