*Identification of prospective participants:* A “recruitment waiver” of the Health Insurance Portability and Accountability Act (HIPAA) authorization from the VA Central Institutional Review Board (CIRB) allows study personnel to screen for prospective participants using approved electronic health information files (corporate data warehouse), rolls of patients attending specific clinics, or medical records, with the assistance of local clinical informatics (IT) personnel as required.

Site study staff may contact a treating healthcare provider to explain the LINK-HF2 study and discuss whether the treating provider believes an identified prospective participant is suitable for participation in the study.

To minimize the possibility of coercion or undue influence. We will explain to the patients and clinicians that they are not obligated to participate in the study. Additionally, we will explain to them that should they choose to become a study participant, they can withdraw any time after enrollment. Furthermore, we will explain to the patient participants that if they decline to participate in the study, their medical care will not be impacted, and they will receive the same medical care as planned before.

To allow adequate time to exchange information and questions between the investigator and participant. We will ensure that the participants clearly understand the study procedure. We will spend adequate time with the participants, to address all questions and concerns the participants may have. Subjects are then scheduled at a mutually convenient time and enrolled.

**Risks:** This is a non-invasive monitoring system in which adhesive surface of a sensor device is placed on the skin of the chest. The possible risks from the device are:

1. Skin irritation due to subjects who may have an allergy to rubber, latex or Band-Aid-type adhesives may experience irritation at the placement of device.
2. Skin damage due to adhesives: Subjects with delicate or thin skin may have skin abrasions or tears when removing the disposable adhesive, The risk of adhesive issues are minimized by advising the patient on methods for safe removal, such as soaking the adhesive patch with hot water, use of rubbing alcohol to dissolve the adhesive, as well as slow and careful removal.

If the reaction is determined to be more than mild by the study team member or by the study patient, the adhesive / device will be removed, and the subject withdrawn from the study.

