## Adverse Event and Serious Adverse Event

Interim analyses. Two interim analyses will be performed, once 50 subjects and 100 subjects complete the study. The main goal of the interim analyses will be monitoring of patient safety. The anticipated possible adverse events fall into two categories: adverse events related to the study sensor and adverse events related to heart failure therapy.

Interim analysis of adverse events related to the study sensor. We will report to the DSMB the rate of AEs related to the study sensor. We anticipate these may include local allergic reaction to the adhesive, skin rash or skin abrasion. While not reported previously, systemic allergic reaction to the adhesive could also occur.

Interim analysis of adverse events related to heart failure therapy. The study intervention is expected to improve clinical outcomes in subjects with heart failure. However, since the algorithmic response triggered by a study alert calls for changes in heart failure therapy or changes in follow-up, there could be adverse events related to these changes triggered by study procedures.

The following events will be recorded, adjudicated and reported to the data coordinating center: - Over diuresis

- Hypotension induced by heart failure medications
- Other adverse events attributed to HF therapy
- Hospitalization

Reporting of interim analyses. The data coordinating center will tabulate the rates of adverse events at the time of the interim analyses.

Adverse events related to the study sensor will be presented for all study subjects, since all study subjects will wear the sensor regardless of randomization assignment. Adverse events related to

heart failure therapy will be tabulated by randomization assignment. This information will be generated by the data coordinating center and provided to the DSMB. The detailed data by randomization group will not be shared with study investigators unless a protocol modification is deemed necessary by the DSMB.

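### Known adhesive allergy is named as a device risk but is not an exclusion, and no allergy check before randomization is described

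*Combined protocol and SAP*

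**What the plan says.** **Eligibility.** The exclusion list in Section 5.4 has one skin-related item: "Skin damage or significant arthritis, preventing wearing of device". The Abstract words it as "skin damage preventing use of study device". Neither mentions allergy. The inclusion criteria do not mention it either; they ask only, in general terms, that the patient be willing and able to carry out the study procedures.

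**Risks.** Section 5.2 lists two device risks, each tied to a type of patient. The first is that "subjects who may have an allergy to rubber, latex or Band-Aid-type adhesives may experience irritation at the placement of device". The second is "Subjects with delicate or thin skin may have skin abrasions or tears when removing the disposable adhesive". The response to a reaction follows: "If the reaction is determined to be more than mild by the study team member or by the study patient", then "the adhesive / device will be removed, and the subject withdrawn from the study".

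**Adverse events.** Section 6.0 (Adverse Event and Serious Adverse Event) expects that sensor-related events may include a local allergic reaction to the adhesive. It adds that "systemic allergic reaction to the adhesive could also occur", and the same sentence says that this has not been reported before. Sensor events go to the DSMB at two interim analyses.

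**Exposure.** All subjects in both arms wear the sensor (Section 6.0). Section 5.0 aims for nearly continuous wear, with subjects replacing mailed adhesive at home, for up to 90 days. Randomization is at enrollment (Section 3.0, Aim 2a).

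**The concern.** The protocol identifies a type of patient for whom the patch may cause a reaction, and the trait can often be read from the chart. Yet the eligibility list does not use it. A patient with a recorded adhesive allergy and undamaged skin is not caught by any written exclusion. That patient could be randomized, fitted with the patch and observed until a reaction forced its removal.

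At stake is avoidable exposure of a small number of patients in both arms. A more-than-mild reaction also ends participation in the study, not only use of the device, and it does so after randomization.

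**Working it through.** **1. The texts side by side**

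| Question | Where | Answer |
|---|---|---|
| Is allergy named as a device risk? | Section 5.2, Risks | Yes, the first of two |
| Is an allergic reaction anticipated? | Section 6.0 | Local: yes. Systemic: possible, not reported before |
| Is known allergy an exclusion? | Section 5.4; Abstract | No |
| Does another criterion name it? | Section 5.4, inclusion | No |
| Is an allergy check or wear test before randomization described? | Sections 3.0, 5.0, 5.2, 5.3 | No |
| Is there preventive advice? | Section 5.2 | Only on removing the patch |
| What happens after a reaction? | Section 5.2 | Removal and withdrawal if more than mild |

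The removal advice (soaking, rubbing alcohol, peeling slowly) addresses tears and abrasions, which is the second risk. It does not prevent an allergic reaction. Section 5.0 describes supervised practice with spare adhesives after consent, but it does not say whether this comes before randomization or serves as a tolerance test.

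**2. The plan's own precision figures**

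Inputs from Section 5.6: N = 240; at most 25% lost, so 240 × 0.75 = 180; SD of the device-functioning ratio 0.289; 95% confidence. The largest half-width for a proportion is at p = 0.5.

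- Alert proportion, N = 240: 1.96 × √(0.25/240) = 0.0633 (plan: 0.063)
- Alert proportion, n = 180: 1.96 × √(0.25/180) = 0.0730 (plan: 0.073)
- Device-functioning ratio, n = 180: 1.96 × 0.289/√180 = 0.0422 (plan: 0.042)

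All three reproduce.

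**3. How many patients**

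The documents give neither the prevalence of adhesive allergy nor a withdrawal rate for reactions. For scale only, assume that 1% to 5% have a recorded allergy and that half of these react more than mildly:

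- affected: 0.01 × 240 = 2.4 to 0.05 × 240 = 12, or about 2 to 12 patients
- withdrawn: half of that, or about 1 to 6 patients
- planned loss for comparison: 0.25 × 240 = 60 patients

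**4. Effect on precision**

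As a harsh case, add the extra loss on top of the full 25%:

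| Extra loss (assumed) | n left | Alert proportion | Device ratio |
|---|---|---|---|
| 0% | 180 | 0.073 | 0.042 |
| 1% | 178 | 0.073 | 0.042 |
| 5% | 168 | 0.076 | 0.044 |
| 10% | 156 | 0.078 | 0.045 |

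Even the 10% row, which is beyond the assumed range, widens the alert interval by only about 0.005. The 25% allowance may already include such withdrawals.

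**The case against.** The strongest reply is that disclosing a risk does not oblige a trial to exclude everyone who carries it. The protocol states the risk, removes the device if the reaction is more than mild, and reports sensor events to the DSMB. It also leaves patients with thin or delicate skin eligible unless existing damage prevents wear, so both groups are treated alike. This is a fair point. A reader might infer that Sections 5.2 and 5.4 contradict each other; they do not. One is silent on a matter that the other raises.

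Second, there are indirect safeguards. Wearing the patch is the central study procedure, so an investigator could judge an allergic patient unable to comply. Charts are screened, and staff may ask the treating provider whether a patient is suitable. These routes exist, so such patients are not admitted by default. But none of them names allergy, the provider consultation is optional, and the six sites listed in Section 5.1 could apply them differently.

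Third, this is a feasibility study. Excluding patients likely to be intolerant will make wear time and retention look somewhat better, and a screening count will not show how many of them could have tolerated the patch. That cost is real. The count limits it by recording how many were excluded for this reason.

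Fourth, the documents do not say that the patch contains rubber or latex. A blanket exclusion for those allergies could turn away patients who are not at risk from this device. This stands and narrows the fix.

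**Conclusion.** The gap is real and modest. Known adhesive allergy is recognized as a device risk but is not dealt with at eligibility, and the only specific response comes after a reaction. Closing it is worthwhile for participant safety and for uniform screening across sites.

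A reader might infer more than the documents support:

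- **That allergic patients are the only risk group.** Section 5.2 names two.
- **That a systemic reaction is an established hazard.** Section 6.0 calls it possible and says it has not been reported.
- **That these patients will be withdrawn.** Withdrawal follows only a more-than-mild reaction.
- **That wear-time or loss-to-follow-up estimates are materially harmed.** About 1 to 6 withdrawals, on assumed rates, compare with a planned allowance of 60, and the half-widths barely move.

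The finding that the eligibility list is silent rests on the text alone. The counts rest wholly on the assumed 1% to 5% prevalence and the assumed one-half withdrawal rate.

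**What to change.** Reconcile the exclusion list in Section 5.4 with the Risks text in Section 5.2 and the adverse-event text in Section 6.0:

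- Add an exclusion for known allergy, or a prior significant skin reaction, to medical adhesive or to a component actually present in the patch. Name rubber or latex only if the patch contains them.
- State that this is checked against the chart allergy list before randomization.
- Record the number of patients excluded for this reason at screening, so that the pivotal trial knows what share of candidates the patch cannot serve.

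If the sponsor means to keep these patients eligible, the protocol should say so and explain how they are protected.

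The cost is one line in an amendment, one item in a chart review that is already done, and one field in the screening log. N = 240 and the stated precision do not change. The downside is slightly fewer eligible patients, and device-functioning estimates that apply to patients without known adhesive allergy. The amendment should give safety as its reason and should not claim a gain in precision or retention.
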